3.4.2 Secondary/tertiary outcomes

A standard Chi-square test will be used to assess the effect of treatment on binary or categorical outcomes, i.e. 28-day all cause mortality, cause of death, place of death, incidence of a new organ failure, incidence of positive blood cultures.

Frequencies and percentages per arm, an odds-ratio measuring the treatment effect and its 95% CI will also be reported along with the p-value of the chi-square test.

In addition the number of new organ failures will be tabulated per treatment arm - frequencies and percentages for all values 0-5 new organ failures.

Survival time from randomization to day 90 will be analysed using a Log-rank test. The p-values and a hazard ratio with its 95% CI obtained from a Cox proportional hazards model will also be presented. The proportional hazard assumption across treatment arms will be checked graphically using a log-cumulative hazard plot or the addition of a time-dependent covariate to the model. Probability of survival by treatment group will also be presented as Kaplan Meier curves.

Length of stay in the ICU and the hospital will be censored due to early deaths or a stay in the ICU or hospital of greater than 90 days. They will therefore be considered as times to discharge from the respective unit and analysed with a log-rank test. Summary statistics will include the median and the interquartile range computed separately for each treatment arm. These statistics, when available, will account for censoring – see for instance SAS procedure LIFETEST or comparable tools in other packages. Mechanical ventilation and renal replacement therapy are resource consumption measures and treatments that are not performed on all patients. They will be summarized in two ways: number and percentage of patients per arm who received such a therapy and mean (SD) duration in days per treatment arm. If patients are still being treated with mechanical ventilation or renal replacement therapy at the end of study their data will be censored. The use of packed red blood cell transfusion will be summarized as number and percentage of patients per arm who receive packed red blood cells and mean (SD) volume of packed red blood cells per treatment arm. The effect of treatment allocation will be tested using a two-sample t-test or Wilcoxon rank sum test as appropriate.

Analyses adjusted for the same predictors as the primary outcome will also be done for the secondary outcomes as subsidiary analyses. They will be based on a linear, logistic or Cox regression as appropriate depending on the type of outcome.

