1.2 Definition of the efficacy variables

1.2.1 Definition of primary outcomes

The primary endpoint is all cause mortality 90-days post-randomisation. As loss to follow-up is expected to be minimal, missing values will not be imputed.

In the subset of patients with traumatic brain injury (TBI) defined as CT evidence of traumatic brain injury and a last pre-sedation and pre-randomization Glasgow Coma Scale score of less than 14, mortality is not considered to be the most appropriate outcome. Patients with TBI will be included in the analysis of all cause mortality 90-days post-randomization; in addition, in patients with TBI, the extended Glasgow outcome scale (GOSE) measured at 6 months and two years will be assessed.

The extended Glasgow outcome scale has 8 categories;

- 1 = dead
- 2 = vegetative state
- 3 = lower severe disability
- 4 = upper severe disability
- 5 = lower moderate disability
- 6 = upper moderate disability
- 7 = lower good recovery
- 8 = upper good recovery

For the purpose of analysis the score will be condensed into 4 categories:

- 1 - dead or vegetative state
- 2 - severe disability
- 3 - moderate disability
- 4 - good recovery

Loss to follow-up of patients with traumatic brain injury is expected to be somewhat higher than in the overall population but still less than 10%; missing values will not be imputed.

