1.4 Analysis principles

1. All analyses will be conducted on an intention-to-treat basis.
2. All tests are two-sided and the nominal level of α will be 5%.
3. All statistical analyses will be unadjusted except where indicated.
4. Subgroup analyses will be carried out irrespective of whether there is a significant effect of treatment on the primary outcome.
5. We will not impute missing values unless specified otherwise. Where the number of missing observations is substantial, we will report the number of observations used in the analysis. Last observations will not be carried forward for continuous outcomes, e.g. the SOFA scores.
6. P-values will not be adjusted for multiplicity. However the outcomes are clearly categorized by degree of importance (primary to tertiary) and a limited number of subgroup analyses are pre-specified.

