2.3 Treatment allocation

Eligible patients will be randomized to one of the two blood glucose targets using minimization. Two strata will be considered: the type of critical illness (post-operative versus non-operative) and geographic region (Australia and New Zealand versus North America). Centralized randomization will be achieved via a password-protected web-based program.

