2.4 Power

We plan to enrol 6100 patients providing 90% power to detect an absolute decrease in mortality of 3.8% from a baseline of 30% (two-sided alpha <0.05). The study is powered to detect a relative risk reduction of 12.7%, which is 37% of the treatment effect documented in Van den Berghe's first study,¹ this difference is clinically important and if detected would likely lead to widespread change in the practice of glycemetic control in ICU's in Australia, New Zealand, North America and beyond.

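### Censoring ICU and hospital stay at death gives medians for a setting without deaths, and ventilation and renal-replacement days are called censored but analysed by methods that cannot use censoring

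*SAP*

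**What the plan says.** Section 1.2.2 lists four durations among the secondary outcomes: ICU stay, hospital stay, mechanical ventilation and renal replacement therapy. The last two are to be counted over all randomised patients who have data.

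Section 3.4.2 then sets the analysis:

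- **ICU and hospital stay.** "Length of stay in the ICU and the hospital will be censored due to early deaths"; stays longer than 90 days are censored on the same footing. The outcome becomes time to discharge, compared by log-rank test. The median and interquartile range are to allow for censoring, with SAS LIFETEST named as an example.
- **Ventilation and renal replacement.** These are labelled measures of resource consumption and summarised by the number treated and the mean (SD) days per arm. "If patients are still being treated with mechanical ventilation or renal replacement therapy at the end of study their data will be censored". Death is not mentioned. A few lines later, after the transfusion outcome: "The effect of treatment allocation will be tested using a two-sample t-test or Wilcoxon rank sum test as appropriate".

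Adjusted linear, logistic or Cox models follow for the secondary outcomes, again without a rule for death. Section 2.6 limits censoring to genuine loss to follow-up.

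**The concern.** Administrative censoring at day 90 and death differ in kind. A patient alive in the unit on day 90 can still be discharged; a patient who has died cannot. A Kaplan-Meier median that censors deaths treats them as if they would have left at the same rate as those still in the unit.

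The issue is not marginal, because the trial assumes about 30% mortality and is sized to find a difference in it. A clinician who reads the planned median as the usual length of stay would be misled. For ventilation and renal replacement, death can end the count, so a change in mortality alone can move the mean days. The analyst is also told to censor values and then given methods with no place for censoring, so part of the analysis must be improvised.

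**Working it through.** **1. The plan's design figure.** Inputs: "All tests are two-sided and the nominal level of α will be 5" per cent (section 1.4); "We plan to enrol 6100 patients providing 90% power" and "an absolute decrease in mortality of 3.8% from a baseline of 30" per cent (section 2.4). Section 2.3 says "Eligible patients will be randomized to one of the two blood glucose targets using minimization" but gives no ratio, so 1:1 is assumed. No inflation for loss is applied, in line with section 1.2.1: "As loss to follow-up is expected to be minimal, missing values will not be imputed".

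n per arm = [1.960 √(2 × 0.281 × 0.719) + 1.282 √(0.30 × 0.70 + 0.262 × 0.738)]² / 0.038² = 2939, or 5878 in total. With continuity correction it is 2991 per arm, 5982 in total. Power at 3050 per arm is 91.0%. The plan's 6100 is reproduced and is not in question; it supplies the mortality gap of 30.0% versus 26.2% used in step 3.

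**2. What the planned median estimates.** Take constant hazards of live discharge and death with sum 1, and let p be the fraction who die in the unit. Then:

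- Kaplan-Meier median with deaths censored = ln 2 / (1 − p)
- median from the cumulative incidence of live discharge = −ln[1 − 0.5 / (1 − p)]
- median time actually spent in the unit = ln 2

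| p (assumed) | Kaplan-Meier | Cumulative incidence | Ratio | Kaplan-Meier / time spent = 1/(1 − p) |
|---|---|---|---|---|
| 0.10 | 0.770 | 0.811 | 0.950 | 1.11 |
| 0.20 | 0.866 | 0.981 | 0.883 | 1.25 |
| 0.25 | 0.924 | 1.099 | 0.841 | 1.33 |
| 0.30 | 0.990 | 1.253 | 0.790 | 1.43 |

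The planned median is thus shorter than the median time to live discharge and longer than the median time spent in the unit; it estimates neither. Once p reaches 0.25 the cumulative incidence never passes 75%, so its upper quartile does not exist.

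**3. Effect on the comparison of arms.** Simulation of 3050 per arm, 400 replicates, deaths 30% versus 26.2%. Assumptions not in the SAP: time to discharge averages 10 days before any effect of severity, all deaths occur in the unit, and ventilated days are 80% of unit days. HR is the discharge hazard ratio, lower- versus higher-mortality arm, with deaths censored. Medians (days) are in the same order.

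| Scenario | HR | Kaplan-Meier medians | Difference in mean ventilated days | t-test significantly longer |
|---|---|---|---|---|
| (a) Discharge unrelated to death risk | 1.00 | 6.9 v 6.9 | +0.31 | 56% |
| (b) Sicker patients leave later, mild link | 0.989 | 6.5 v 6.4 | +0.39 | 75% |
| (b) Same, strong link | 0.984 | 6.1 v 6.0 | +0.58 | 90% |
| (c) Reverse link | 1.013 | 7.0 v 7.1 | +0.33 | 31% |
| (d) Saved patients leave at the usual rate | 1.055 | 9.4 v 9.9 | +0.01 | 2% |
| (d) Saved patients leave faster | 1.076 | 9.1 v 9.9 | −0.15 | 0% |
| (e) Saved patients stay three times as long | 0.989 | 9.8 v 9.9 | +0.57 | 75% |

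In (b) the log-rank test finds significantly slower discharge in 6.5% to 8.3% of runs, against 2.5% expected. In (d) it finds significantly faster discharge in 42% to 67%. In (e) the test and the median point in opposite directions. If deaths are instead kept in the risk set to day 90, the discharge ratio is 1.08 to 1.11 in every scenario and significant in 67% to 93% of runs.

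**4. Ventilation and renal replacement.** A mean, a t-test and a Wilcoxon test each need one complete number per patient. A censored duration is only a lower bound. Within a fixed 90-day window the count is complete (a patient still treated on day 90 contributes the days up to then), so nothing needs censoring.

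**5. Section 2.6 against section 3.4.2.** The first allows censoring only for genuine loss to follow-up. The second also censors for death, for long stay and for treatment still running. Section 2.6 may have been written with survival time in mind, but it does not say so.

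**The case against.** Much of the other side's case stands.

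- A reader might infer that an arm with fewer deaths must look worse on all four durations. The document does not support that. In step 3 the discharge hazard ratio runs from 0.98 to 1.08, according to links between prognosis and discharge on which the SAP is silent. Ventilated days show no excess when saved patients recover as fast as others or faster.
- A log-rank test with deaths censored is a valid comparison of cause-specific discharge hazards. The fault lies in the median and the missing label, not in the test.
- Days per randomised patient that end at death are a proper measure of resource use, which is what section 3.4.2 calls them. They mislead only if read as benefit or harm. That the count stops at death is itself inferred.
- The t-test sentence follows the transfusion outcome and could be read as covering that alone. Ventilation and renal replacement would then have no named test, and the mean (SD) would still have no way to use censored values.
- Gray's test and free-days fold mortality into the comparison, and mortality is already tested. That is a choice of estimand and a reason to add them rather than substitute them.
- The 30% in section 2.4 is 90-day mortality, which includes deaths outside the unit. In-unit deaths may be fewer, and the 10% row in step 2 shows a gap of only 5%. The planned adjustment for severity may also remove part of any drift in length of stay.

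None of this rescues a median that cannot be read as a length of stay, or a censoring rule that the named methods cannot apply.

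**Conclusion.** The point holds in limited form. The planned medians and interquartile ranges for ICU and hospital stay describe a setting without deaths. Under constant hazards they are 12%, 16% or 21% shorter than the median time to live discharge when 20%, 25% or 30% die in the unit. Those fractions and the constant hazards are assumptions. The instruction to censor ventilation and renal-replacement durations cannot be carried out with the methods named, and death has no rule there.

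All four arm comparisons are entangled with mortality, but no direction can be stated beforehand. The medians in step 2 concern the level within an arm; in that same setting, scenario (a), there is no difference between arms.

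This is an improvement to secondary outcomes. Neither the primary test nor the stopping rule depends on it.

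**What to change.** 1. **ICU and hospital stay.** Report the median and quartiles from the cumulative incidence of live discharge, with death as a competing event, and state not reached where a quartile does not exist. Keep the log-rank test, labelled as a comparison of cause-specific discharge hazards, and show Gray's test beside it.
2. **Ventilation and renal replacement.** Replace the censoring sentence: count days of each therapy from randomisation to the earlier of death or day 90, per randomised patient with data, labelled as resource use. Add days alive and free of each therapy to day 90, with death by day 90 scored 0, compared by Wilcoxon test, and show deaths and treated days separately.
3. **Censoring rule.** Reconcile sections 2.6 and 3.4.2, stating which outcomes each rule governs.

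The cost is SAP wording and standard software. Section 2.1 already collects dates of death and discharge and daily therapy status. The daily form covers ICU days only, so the SAP must state that days outside the ICU count as free of therapy. The small downside is that the free-days and cumulative-incidence comparisons include the mortality effect and must be read with it.

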3.4.3 Safety outcomes

1. Severe hypoglycemia: Number of patients with blood glucose (BG) ≤ 2.2 mmol/L (≤ 40 mg/dL) in the ICU during the 90-day study period.
 - a. Number of episodes of BG ≤ 2.2 mmol/L (≤ 40 mg/dL) per patient
 - b. Number of patients with clinical sequelae of severe hypoglycemia
 1. Neurological sequelae
 2. Cardiovascular sequelae
 3. Other sequelae

Number of episodes of severe hypoglycemia (measured blood glucose concentration ≤ 2.2 mmol/L or ≤ 40 mg/dL) at any time in the ICU and incidence of clinical consequences of severe hypoglycaemia (Neurological, Cardiovascular and Other), will be compared between groups using a Chi squared statistic or Fisher's exact test, with odds ratios and 95% CI when these quantities are computable. Frequencies and percentages per treatment group will be presented. Adjusted analysis will not be performed for safety endpoints.

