1.3 Definition of the safety variables

Hypoglycaemia is the main adverse event and safety issue in the study. Previous studies suggest that employing strict glycaemic control in a population of Intensive Care patients will result in between 5 and 42 episodes of severe hypoglycemia for every 100 patients recruited to the lower range group and less than 5 episodes of severe hypoglycemia for every 100 patients recruited to the higher range group. The incidence of severe hypoglycemia and clinical consequences of severe hypoglycemia will be compared across treatment arms.

1. Number of patients suffering severe hypoglycemia (documented blood glucose concentration of 2.2mmol/L or less [40mg/dL or less] at any time in the ICU within 90-days of randomization) and number of episodes of severe hypoglycaemia occurring in the ICU within 90-days of randomization.
2. Incidence of clinical consequence of severe hypoglycemia
 - I. Neurological
 - II. Cardiovascular
 - III. Other

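### Section 3.4.3 assigns a chi-squared or Fisher test with an odds ratio to the number of hypoglycaemia episodes, which can recur within a patient, and names no test for the number of patients affected

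*SAP*

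**What the plan says.** SAP section 1.3 states: "Hypoglycaemia is the main adverse event and safety issue in the study". Its first safety item holds two separate quantities: the number of patients with severe hypoglycaemia, and the "number of episodes of severe hypoglycaemia occurring in the ICU within 90-days of randomization". Section 3.4.3 keeps them apart. The patient count is the parent item, and episodes per patient is a sub-item, so more than one episode per patient is foreseen.

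The only sentence in section 3.4.3 that names a test opens with "Number of episodes of severe hypoglycemia (measured blood glucose concentration". It adds the incidence of clinical consequences and says that these "will be compared between groups using a Chi squared statistic or" the exact test of Fisher. The effect measure is then promised subject to a condition: "with odds ratios and 95% CI when these quantities are computable". The sentence names no test for the number of patients affected and no method for a count.

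Section 1.3 also gives expected frequencies. For tight control it cites "between 5 and 42 episodes of severe hypoglycemia for every 100 patients recruited to the lower range group". In the other arm it expects fewer than 5 per 100.

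**The concern.** A 2×2 chi-squared or Fisher test, and the odds ratio that goes with it, need one independent yes/no result per unit. A patient who has had one severe episode may well have another, so episodes do not meet that condition. A percentage of episodes also has no natural denominator.

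If the analyst divides episodes by patients, the binomial variance used by the test is smaller than the true variance of the episode count. The p-value is then too small and the interval too narrow. The odds ratio itself has no clear meaning, because an episode is not an outcome that a patient either has or lacks.

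What is at stake is how precisely the excess of hypoglycaemia is reported, in a trial where that excess is the chief safety question. There is also a gap: the patient-level count, which readers will look at first, has no named test.

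**Working it through.** **Inputs**

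- Total sample 6100 (section 2.4). The allocation ratio is not stated, so 3050 per arm is an assumption. As a check on that input, 30% versus 26.2% mortality with 3050 per arm gives 91.0% power, consistent with the stated 90%. The SAP gives no power or precision figure for hypoglycaemia, so there is nothing further to reproduce.
- Episode rates (section 1.3): 5 to 42 per 100 in the lower range arm, less than 5 per 100 in the higher range arm.
- Clustering: not given. It is expressed as φ, the variance-to-mean ratio of episodes per patient. Values of 1 (Poisson), 1.25 and 2.0 are assumed. With negative binomial counts at 5 per 100, these correspond to about 1.03, 1.15 and 1.47 episodes per affected patient.

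**False-positive rate when the arms do not differ**

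The only common rate near both stated expectations is about m = 0.05 episodes per patient.

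- Variance used by the 2×2 test: 2m(1 − m)/n
- True variance of the difference in episodes per patient: 2φm/n
- Effective critical value: 1.96 × √[(1 − m)/φ]

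| φ | Effective critical value | Type I error, formula | Type I error, simulated |
|---|---|---|---|
| 1 | 1.96 × √0.95 = 1.910 | 5.6% | 5.5% |
| 1.25 | 1.96 × √0.76 = 1.709 | 8.8% | 8.8% |
| 2.0 | 1.96 × √0.475 = 1.351 | 17.7% | 17.6% |

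The simulation used 100,000 trials per row. Separate runs of 20,000 gave 5.6% to 5.7%, 8.7% to 9.0% and 17.0% to 17.5%.

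**Interval coverage when there is a real difference**

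Take 20 versus 4 episodes per 100, an illustration inside the expected ranges. The odds ratio computed from episodes over patients is (0.20/0.80)/(0.04/0.96) = 6, so its logarithm is 1.792.

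- Variance used: [1/(0.20 × 0.80) + 1/(0.04 × 0.96)]/n = 32.29/n, giving a standard error of 0.103
- True variance (delta method): φ[1/(0.20 × 0.80²) + 1/(0.04 × 0.96²)]/n = 34.94φ/n
- Effective multiplier: 1.96 × √[32.29/(34.94φ)]

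| φ | Effective multiplier | Coverage, formula | Coverage, simulated | z with the true variance |
|---|---|---|---|---|
| 1 | 1.884 | 94.0% | 94.1% | 16.7 |
| 1.25 | 1.685 | 90.8% | 90.9% | 15.0 |
| 2.0 | 1.332 | 81.7% | 81.7% | 11.8 |

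The difference stays far beyond any significance threshold. Only the interval is wrong.

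**Patient-level tests, no difference between arms**

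- Chi-squared on patients with at least one episode, with 5%, 10% or 20% affected: type I error 5.0%, 5.2% and 5.4%.
- Chi-squared on patients classed as 0, 1 or 2+ episodes: 5.2% to 5.4%.

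Both hold the nominal level.

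**The case against.** The strongest defence is that a patient-level comparison was meant. Section 3.4.3 puts patients first, lists episodes per patient beneath them, and asks for frequencies and percentages. Section 1.3 speaks of comparing incidence. The qualifier about computability could suit a table of patients with 0, 1 or 2+ episodes, where no single odds ratio exists. The SAP never says outright that total episodes are divided by patients. This is a fair reading, and under it the test is valid. But section 3.4.3 does not state it, and a statistician following the sentence as written would test episodes.

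The second defence is that the expected difference is too large for the p-value to matter. That stands for significance over most of the expected range. It does not rescue the confidence interval, which the plan also promises.

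A reader might also infer more than the document supports:

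- **That all hypoglycaemia results are invalid.** They are not. The same test is sound for patients affected and for patients with sequelae.
- **That the false-positive rate reaches 39%.** That figure needs 42 episodes per 100 in both arms plus heavy clustering. Section 1.3 gives 42 as the upper end for the lower range arm only, and less than 5 for the other arm.
- **That ignoring time at risk, or reporting an odds ratio rather than a relative risk for patients, is an error.** Section 1.3 frames the outcome per patient, and the SAP uses odds ratios for binary outcomes elsewhere. An ICU-day denominator is itself a post-randomisation outcome. These are preferences.

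**Conclusion.** The sentence is wrong as written: a test and effect measure for binary data are assigned to a recurrent count, and the patient count that suits them is left without a named test. The harm is confined to the episode comparison and arises only if the sentence is followed literally.

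At about 5 episodes per 100 with no difference, the nominal 5% test rejects about 6% to 17.5% of the time for variance-to-mean ratios of 1 to 2. With few repeats the error is small. At 20 versus 4 per 100, coverage of the 95% interval falls to between 94% and 82% over the same range, while significance is not in doubt. These sizes rest on 3050 per arm and on assumed clustering. The direction does not depend on the clustering value, since even Poisson counts exceed the nominal level slightly.

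The primary outcome is untouched.

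**What to change.** Reword section 3.4.3 so that each quantity has its own method:

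- **Patients.** Apply chi-squared or Fisher, with odds ratio and 95% CI, to the number of patients with at least one severe episode and to the number with each type of sequela.
- **Episodes.** Compare episodes per patient with a method that allows for repeats. Either use a rate ratio per randomised patient from a negative binomial model or with robust variance, or use a Wilcoxon test on episodes per patient, which section 3.4.2 already allows for per-patient durations and volumes. Drop the chi-squared test and odds ratio for episodes.
- **Optional.** A rate per ICU-day may be added as a supplementary analysis.

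The cost is a change of wording, one more standard analysis, and a wider interval for episodes. The hypoglycaemia form in section 2.1 already records the number of episodes, so no new data are needed. The change should be made before the statisticians are unblinded.
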